2.4. Siltuximab Treatment Date

Siltuximab treatment date is the date on which a subject actually received siltuximab (partial or complete) administration.

For subjects who previously received siltuximab treatment, the first siltuximab treatment date is defined as the earliest date of non-zero dose of siltuximab administration from study C0328T03 or CNTO328MCD2001. The last study treatment date is defined as the latest date of non-zero dose of siltuximab administration from CNTO328MCD2002.

For subjects who were siltuximab-naive, the first study treatment date is defined as the earliest date of non-zero dose of siltuximab from study CNTO328MCD2002. The last study treatment date is defined as the latest date of non-zero dose of siltuximab administration from study CNTO328MCD2002.

2.5. Imputation of Partial Dates

Unless specified otherwise, no data imputation will be applied for missing safety and efficacy evaluations. For analysis and reporting purpose, partial dates in adverse event (AE onset date; AE end date), concomitant therapies (start date; end date), MCD diagnosis date, prior MCD therapies (start date; end date) and start date of subsequent MCD therapy will be imputed.

The detailed imputation rules along with other derived variables are specified in the data presentation specification (DPS).

2.6. General Analysis Method

In general, continuous variables will be summarized using descriptive statistics such as mean, standard deviation (SD), median and range. Categorical variables will be summarized using frequency and percentage. For time-to-event variables, the Kaplan-Meier method will be used for descriptive summaries. For the calculation of time-to-event and duration-of-event variables, the difference between the start date and the end date plus 1 day will be used.

2.7. Analysis Sets

Safety population is defined in this study. The safety population will include subjects who have received at least 1 administration of siltuximab treatment (partial or complete). This analysis population will be used for all analyses.

3. INTERIM ANALYSIS

No later than 2 years after start of enrollment, an interim analysis will be conducted to further evaluate the benefit and safety of long-term treatment with siltuximab in subjects with MCD. In addition, the interim analysis results will be used to support internal decision-making.

4. SUBJECT INFORMATION

4.1. Demographics and Baseline Characteristics

Because demographics and baseline disease characteristics were not collected in the current long-term safety extension study of CNTO328MCD2002, therefore, demographics and baseline characteristics variables will be summarized based on data collected in the parent study of C0328T03 or CNTO328MCD2001.

Subject demographic and baseline characteristic variables: age (<65 years; ≥65 years), sex, race, weight (kg), height (cm) and ECOG performance score will be summarized.

Baseline disease characteristics including Castleman's disease histology (hyaline vascular; plasmacytic, mixed, undetermined) based on local pathology review, type of disease (unicentric, multicentric), HHV-8 status (positive, negative), and years since disease diagnosis (years) will be tabulated.

The distribution of subject enrollment to the long-term safety extension will be presented according to region and country. Subjects who did not meet inclusion/exclusion criteria for long-term extension study will be listed by subject ID and specific criteria not met.

4.2. Disposition Information

An overview of subject disposition in the long-term safety extension study will be provided. The overview includes number of subjects who previously enrolled to study C0328T03, or CNT0328MCD2001, for subjects who were previously in the study CNT0328MCD2001, a total number of subjects who were in siltuximab arm or placebo arm will be provided, respectively. Among all treated subjects (defined as subjects who have received at least 1 administration of siltuximab treatment), the number and percentage of subjects who discontinued siltuximab treatment including reason for discontinuation as indicated in the “End of Treatment” CRF page will be summarized.

Similar summaries will be presented for all treated subjects who discontinued study (i.e., CNT0328MCD2002).

In addition, a listing of subjects who discontinued siltuximab treatment/study with reason for discontinuation will be provided, separately. The listing may include subject ID, date of siltuximab discontinuation, reason for discontinuation, if reason for discontinuation is due to adverse event, the AE leading to discontinuation will be provided as well.

4.3. Extent of Exposure

Long-term treatment with siltuximab will be summarized and presented based on the safety population by combining parent study and extension study.

Duration of study treatment, defined as the number of years from the date of the first administration of siltuximab treatment to the date of the last administration of siltuximab treatment, will be summarized by descriptive statistics. In addition, the number and percentage of subjects who were on siltuximab treatment for more than 1, 2, 3, 4, 5, 6, 7 and 8 years will be provided.

The total number of siltuximab administrations including cumulative dose (mg/kg) administered across both parent and extension studies will be summarized.

The number of subjects with siltuximab dose delays including reasons (AE or other) for dose delays in the long-term safety extension study of CNT0328MCD2002 will be reported.

4.4. Protocol Deviations

A listing of subjects with major protocol deviations during the long-term safety extension study will be provided. The listing will include subject ID, type of deviation, and reasons for deviation.

4.5. Prior Therapies for Castleman’s Disease

A summary of type of prior therapies (systemic therapy, ASCT, radiotherapy, or cancer-related surgery) for Castleman’s disease will be provided. Specifically, for subjects who received prior systemic therapy, the number of prior therapy regimen will be calculated

and summarized by the following categories: 1, 2, 3, 4 or >4 through frequency and descriptive statistics. In addition, the summary of prior systemic therapies will be presented by the following therapy: cyclophosphamide, rituxan, steroid and thalidomide.

Additionally, the best response to last prior systemic therapy based on investigator assessment will be summarized. Time in days from last prior systemic therapy to the first siltuximab administration will be calculated.

4.6. Concomitant Medications

Concomitant medications reported when subject received siltuximab treatment will be summarized by therapeutic class, pharmacologic class, and drug name. In addition, systemic steroids as concomitant medication use during the study will be summarized.

4.7. Subsequent MCD Therapy

The total number of subjects who received subsequent MCD therapy will be reported. A summary of subsequent anticancer therapy will be presented by therapeutic class, pharmacologic class and drug name.

5. EFFICACY

There is no formal statistical hypothesis testing. All efficacy analyses will be based on safety analysis population.

5.1. Analysis Specifications

5.1.1. Level of Significance

All 95% confidence intervals presented will be 2-sided.

5.1.2. Data Handling Rules

There is no imputation planned for missing efficacy endpoint values.

5.2. Efficacy Endpoints

The efficacy endpoints include proportion of previously responding subjects who maintain disease control, proportion of siltuximab-naive subjects who experience disease control, duration of disease control and overall survival.

5.2.1. Proportion of Subjects Maintaining Disease Control

5.2.1.1. Definition

Proportion of subjects maintaining disease control is defined as the proportion of previously responding subjects who have not progressed during the long-term safety extension based on investigator assessment.

5.2.1.2. Analysis Methods

The number and percentage of subjects who maintain disease control will be provided.

5.2.2. Proportion of Subjects Experiencing Disease Control

5.2.2.1. Definition

Proportion of subjects experiencing disease control is defined as the proportion of siltuximab-naïve subjects who have stable or better response during the long-term safety extension based on investigator's judgment.

5.2.2.2. Analysis Methods

The number and percentage of subjects who experience disease control will be provided.

5.2.3. Duration of Disease Control

5.2.3.1. Definition

For subjects who had/experienced disease control, duration of disease control (DODC) is defined as the time from the first siltuximab administration to disease progression as assessed by the investigator. Subjects with disease control are subjects who had stable or better response assessed by the investigators. Subjects without disease progression will be censored at the date of last disease assessment. Note that disease control was only collected in long-term safety extension study of CNT0328MCD2002.

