### 4.2 Inclusion Criteria

Potential subjects must satisfy all of the following criteria to be enrolled in the study:

1. Subjects must have multicentric Castleman's disease.
2. Subjects must have previously been enrolled in study C0328T03 or CNTO328MCD2001 (either treatment arm).
3. Subjects must have had their last administration of study treatment (siltuximab or placebo) less than 6 weeks (window of plus 2 weeks) prior to first dose. Subjects with longer treatment durations since the last study treatment may be allowed after discussion with the medical monitor.
4. Subjects must not have had disease progression while receiving siltuximab. For those subjects originally assigned to placebo in the CNTO328MCD2001 study, subjects who have received less than 4 months of siltuximab following crossover will also be eligible.
5. Adequate clinical laboratory parameters within 2 weeks prior to the first dose of siltuximab for this protocol:
  - a. Absolute neutrophil count (ANC) greater than or equal to  $1.0 \times 10^9/L$  ( $1,000/mm^3$ ) with or without neutrophil growth factors

- b. Platelets greater than or equal to  $50 \times 10^9/L$  ( $50,000/mm^3$ ) with or without platelet transfusion, thrombopoietic cytokines, or both
  - c. AST, ALT, total bilirubin and alkaline phosphatase must be within 2.5 x ULN; if alkaline phosphatase is above that, at least alkaline phosphatase liver fraction has to be less than or equal to 2.5 x ULN
6. Any other clinical significant toxicity must be less or equal to Grade 2 or the baseline value of the previous study.
  - 7.1 Women of childbearing potential must agree to use adequate birth control measures during the study and for 3 months after receiving the last dose of study agent, and must have a negative pregnancy test (serum or urine beta-human chorionic gonadotropin [ $\beta$ -HCG]) at screening. Men must agree to use a double barrier method of birth control and to not donate sperm during the study and for 3 months after receiving the last dose of study agent.
  8. Sign an informed consent document indicating that they understand the purpose of and procedures required for the study and are willing to participate in the study.

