**11.4 Efficacy and Patient-reported Outcomes Analyses****11.4.1 Disease Control**

Investigator assessment of disease control for all treated subjects will be analyzed. Specifically, the proportion of previously responding subjects and siltuximab-naïve subjects who maintain disease control will be summarized. The duration of disease control, defined as the time from the first siltuximab administration to disease progression as assessed by the investigator, will also be summarized.

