**11.4.3 Overall Survival**

Overall survival is defined as the time between the first study siltuximab administration and death. Subjects who died, regardless of the cause of death, will be considered as an event. Subjects who withdraw consent from the study will be censored at the time of withdrawal. Subjects who are still alive at the cutoff date of the final analysis will be censored at the date of last known alive. All subjects who are lost to follow-up before the 6-year data cutoff will be censored at the date they are last known to be alive.

The Kaplan-Meier method will be used to estimate the distribution of overall survival. Median overall survival with 95% CI will be provided. In addition, the Kaplan-Meier overall survival curve will also be provided.

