2.2. Study Data to Be Included in Analysis Tabulation

Subjects treated in the long-term safety extension study of CNTO328MCD2002 were previously enrolled in sponsor-initiated studies of MCD, therefore demographics, baseline characteristics, and prior systemic therapy data will come from parent study of C0328T03 or CNTO328MCD2001. Overall treatment exposure, safety evaluations (i.e., adverse events), and overall survival will be based on parent study and extension study. The data included in these overall summaries are from the start of C0328T03 or CNTO328MCD2001 to the end of CNTO328MCD2002.

Due to quite different schedules in laboratory assessment and vital sign collection between parent study and long-term safety extension study, safety evaluation through laboratory assessment and vital signs will focus on long-term safety extension study of CNTO328MCD2002. Similarly, immunogenicity analyses will also be based on long-term safety extension study.

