5.2.3.2. Analysis Methods

Analysis of duration of disease control will be based on Kaplan-Meier method, median DODC with 95% CI will be estimated. The Kaplan-Meier duration of disease control curve will be plotted.

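### SAP 5.2.3.1 does not name the study in which duration of disease control starts; if it starts at the parent-study first dose, as SAP 2.4 suggests, ordinary Kaplan-Meier overstates it

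*SAP*

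**What the plan says.** **Start and end of the interval.** SAP 5.2.3.1: "For subjects who had/experienced disease control, duration of disease control (DODC) is defined as the time from the first siltuximab administration to disease progression". Subjects who have not progressed are censored at their last disease assessment. The same section adds: "Note that disease control was only collected in long-term safety extension study". Protocol 11.4.1 has the same unqualified start ("defined as the time from the first siltuximab administration to disease progression as assessed by the investigator"). For survival, by contrast, Protocol 11.4.3 adds the word study: "Overall survival is defined as the time between the first study siltuximab administration and death".

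**Which date that is.** SAP 2.4 says that, for previously treated subjects, "the first siltuximab treatment date is defined as the earliest date of non-zero dose of siltuximab administration from study C0328T03 or CNTO328MCD2001". For siltuximab-naive subjects it is the first dose in CNTO328MCD2002.

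**Which analyses join the two studies.** SAP 2.2: "Overall treatment exposure, safety evaluations (i.e., adverse events), and overall survival will be based on parent study and extension study". DODC is not in that list.

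**Estimator.** SAP 5.2.3.2: "Analysis of duration of disease control will be based on Kaplan-Meier method, median DODC with 95% CI will be estimated", with a plotted curve. Delayed entry to the risk set is not mentioned.

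**Who could enter.** Protocol 4.2, criterion 4: "Subjects must not have had disease progression while receiving siltuximab". Placebo subjects who crossed over and had under 4 months of siltuximab are admitted by a separate sentence. Protocol 4.3, criterion 1, excludes those who stopped parent-study treatment because of progression. Protocol 3.1 expects up to 75 subjects, most of them already on siltuximab.

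**The concern.** Two programmers could derive different start dates from this text. The choice matters because entry to the extension was conditional on not having progressed. If the clock starts at the parent-study first dose, a previously treated subject brings months or years in which the event could hardly have been observed: anyone who progressed in that period is not in the data set. Ordinary Kaplan-Meier puts these subjects in the risk set from day 0. The denominator is then inflated over the lead-in period and the curve stays too high.

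Describing the duration of disease control is a stated secondary objective. There is no comparator, so this curve is the study's time-to-event answer on how long control lasts.

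**Working it through.** The documents give no expected DODC, event count or power, so there is no planned figure to reproduce. The check is a reading of the definitions followed by an illustration of size.

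**1. Which start date?**
- For the parent dose: SAP 2.4 is the only place where the SAP defines a first siltuximab date. SAP 4.3 also counts exposure from first siltuximab across both studies.
- For the extension dose: SAP 2.2 omits DODC; control was collected only in the extension; the two companion proportions (SAP 5.2.1.1 and 5.2.2.1) refer to the extension period.
- Neither reading is excluded. SAP 2.4 makes the parent dose the more natural one.

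**2. Inputs for the size.** From the documents: 331 days, the median C0328T03 exposure reported in Protocol 1.1.2.1. That is not the prior exposure of extension entrants, so its use as a lead-in *L* is an assumption. Also assumed are the progression hazard *h*, its shape and the naive share *v*. Protocol 3.1 says only that the majority are on siltuximab, so *v* is ranged from 0% to 49%. *L* = 331/365.25 = 0.906 years = 10.9 months.

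**3. Median.** With constant hazard, a common lead-in and no naive subjects, ordinary Kaplan-Meier on the parent clock gives S(t) = 1 up to *L* and exp(−h(t − L)) after it. The median is L + ln 2/h instead of ln 2/h: too long by exactly *L*, or 10.9 months here. With a naive share *v* the excess is ln[v + (1 − v)e^(hL)]/h, if the median falls after *L*:

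| True median (assumed) | v = 0% | v = 25% | v = 49% |
|---|---|---|---|
| 24 months | +10.9 | +8.5 | +6.0 |
| 48 months | +10.9 | +8.3 | +5.8 |

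At h = 0.10 per year the true median is ln 2/0.10 = 6.9 years and may not be reached. The next step therefore uses a fixed time. SAP 5.2.3.2 does not plan a fixed-time DODC rate; it serves here only to show the height of the curve.

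**4. Curve at 3 years.** Truth: exp(−3h). Previously treated subjects on the parent clock: exp(−h(3 − L)). Pooled excess: (1 − v)[exp(−h(3 − L)) − exp(−3h)].

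At h = 0.10: exp(−0.300) = 0.741 and exp(−0.209) = 0.811, a difference of 0.070. Excess: 7.0 points at v = 0%, 5.6 at 20%, 4.7 at 33%, 3.6 at 49%.

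At h = 0.05: 0.901 − 0.861 = 0.040, so 4.0 points (v = 0%) to 2.0 (v = 49%). At h = 0.20: 0.658 − 0.549 = 0.109, so 10.9 to 5.6 points.

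A 2-year lead-in at h = 0.10: 0.905 − 0.741 = 0.164, so 16.4 to 8.4 points. SAP 4.3 plans an exposure category above 8 years against a cutoff about 6 years after first enrolment. That implies 8 − 6 = 2 or more years of earlier treatment for some subjects, not for a typical one.

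**5. Does the direction depend on the hazard shape?** Take a Weibull with true 3-year control held at 74.1%, v = 20% and L = 331 days. The parent clock gives v·S(3) + (1 − v)·S(3)/S(L) = 83.4% for a falling hazard (shape 0.6), 79.7% for a constant one and 77.1% for a rising one (shape 1.5). All are above 74.1%.

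**6. The extension clock.** It estimates v·S(3) + (1 − v)·S(3 + L)/S(L), which in the same three cases is 80.0%, 74.1% and 68.7%. There is no selection bias for control after entry, but this is a different quantity from control since first dose. The two agree only under a constant hazard.

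**The case against.** The strongest reply is that the documents show an ambiguity, not a biased analysis. SAP 2.2, the note on where control was collected and the wording of the companion endpoints all fit an extension start. SAP 2.5 also says that derived variables are specified in a separate data presentation specification, which may settle the date. This stands to the extent that the bias is conditional. It does not close the point: nothing shown overrides SAP 2.4, and a time zero belongs in the SAP.

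A second reply is that pre-entry control was real time for those who entered, and that SAP 5.2.3.1 already restricts DODC to subjects with control. That is true of each entrant. But those who progressed in the parent study are missing from the risk set, so the curve does not estimate control from first siltuximab dose, which is what its definition describes. The restriction to controlled subjects is a further selection that the figures above do not model.

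A third is that the endpoint is secondary and descriptive, without a hypothesis test, beside a primary safety objective. That limits the consequence.

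A reader might also infer that the pooled parent-dose curve mixes two clocks. It does not: under SAP 2.4 everyone is timed from first siltuximab. What differs is when each subject came under observation.

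**Conclusion.** The point holds as a gap in the definition with a conditional bias, and it should be fixed. SAP 5.2.3.1 does not say which first dose starts DODC. If it is the parent-study dose, ordinary Kaplan-Meier overstates control from first siltuximab dose. The direction follows from the entry criteria, with one reservation: criterion 4 leaves unclear whether placebo crossovers are an exception to the no-progression rule, but their lead-in is under 4 months.

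The size is not known. The figures of about 11 months on the median, and 3.6 to 7.0 points at 3 years, rest on an assumed 331-day lead-in and a constant hazard (10% per year for the latter). They grow with the lead-in and shrink with the naive share.

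A reader might go further and conclude that the SAP commits to a biased estimate, or that the bias is as large as the 2-year case. The documents support neither: the extension-dose reading remains open and is free of this bias, and entrants' prior exposure is not reported.

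**What to change.** State in SAP 5.2.3.1 that time zero for DODC is the first CNTO328MCD2002 dose. Show previously treated and siltuximab-naive subjects as separate curves, and label the previously treated curve *further disease control after extension entry*.

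If duration from the parent-study first dose is also wanted, use Kaplan-Meier with entry to the risk set at the first CNTO328MCD2002 dose, print numbers at risk, and label any part that starts after time zero as conditional on control to that time.

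**Cost.** SAP wording and small programming changes, on dates that the exposure summary already needs. Reported durations will be shorter. Groups per curve are smaller: with an assumed 60 and 15 subjects and 74.1% control, the standard error √(0.741 × 0.259/n), ignoring censoring, is 5.7 and 11.3 points, against 5.1 for all 75.

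The delayed-entry version is weak early on. If prior time among 60 previously treated subjects were uniform from 0 to twice its mean, the number entered by 3 months would be 60 × 0.25/1.81 ≈ 8 (mean 331 days) or 60 × 0.25/4 ≈ 4 (mean 2 years). Simulated standard deviations of their 3-year estimate were 9.6 and 13.2 points (10% per year progression, 5% per year other exit, 4 to 6 years of potential follow-up, all assumed). If all had the same prior time, nobody would be at risk before it, and delayed entry could not correct that curve; it could only be read as conditional. This is why the extension dose is the better main time zero.

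### SAP 5.2.3.1 limits duration of disease control to subjects who achieved control but times it from first dose, so never-controlled subjects are dropped and the curve is modestly too high

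*SAP*

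**What the plan says.** SAP 5.2.3.1 defines the endpoint as follows: "For subjects who had/experienced disease control, duration of disease control (DODC) is defined as the time from the first siltuximab administration to disease progression". It then says who qualifies: "Subjects with disease control are subjects who had stable or better response assessed by the investigators". It adds "Note that disease control was only collected in long-term safety extension study", and on censoring: "Subjects without disease progression will be censored at the date of last disease assessment".

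The start date comes from SAP 2.4. For previously treated subjects "the first siltuximab treatment date is defined as the earliest date of non-zero dose of siltuximab administration from study C0328T03 or CNTO328MCD2001"; for siltuximab-naive subjects "the first study treatment date is defined as the earliest date of non-zero dose of siltuximab from study CNTO328MCD2002". SAP 5.2.3.2 plans one Kaplan-Meier curve with a median and 95% CI, and no landmark.

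Protocol 11.4.1 opens with "Investigator assessment of disease control for all treated subjects will be analyzed" and then defines the duration without any condition on achieved control: "The duration of disease control, defined as the time from the first siltuximab administration to disease progression as assessed by the investigator, will also be" summarised. Protocol 11.1 and SAP 2.7 use the safety population for all analyses, and SAP Section 5 repeats this for efficacy.

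**The concern.** Entry to the analysis depends on something observed after the clock has started. A subject who takes siltuximab and is only ever assessed as progressing has the shortest possible duration, yet under the SAP contributes nothing. Removing early events while still timing from first dose makes later estimates too favourable.

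The restriction also conflicts with the SAP's own analysis-set rule, so two programmers could arrive at different denominators. Duration of disease control is named in a secondary objective, and its median and interval are what will be reported.

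**Working it through.** **There is no plan figure to reproduce.** The documents give no expected duration, event count or early-progression rate. The direction follows from the definition; the size needs assumptions.

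**Inputs**
- Pooled subjects: up to 75 (Protocol 11.2).
- Assessments: screening, Cycles 4, 7 and 10, then every 6 months (Protocol 9.3.1). On 3-week dosing Cycle 4 falls 3 × 21 = 63 days after the first extension dose.
- Number dropped, k: not given; k = 1, 3 and 5 are assumed.
- Siltuximab-naive subjects: not given. About 78 were to be randomised 1:2 to placebo or siltuximab in CNTO328MCD2001 (Protocol 1.1.2.2), so 78 × 1/3 = 26 is a ceiling.

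**Formula.** Suppose k of N subjects progress at their first on-treatment assessment, before any other event or censoring, and never qualify as controlled. The all-treated curve steps down to (N-k)/N at that point. Afterwards both analyses have the same risk sets, so at later times:

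S_all(t) = (1 - k/N) × S_SAP(t), and relative overstatement = N/(N-k) - 1.

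This is zero when k = 0 and positive otherwise.

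**Pooled curve, as the SAP plans (N = 75)**

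| k | Overstatement | Reported 90% is, in all treated | All-treated level at the reported median |
|---|---|---|---|
| 1 | 75/74 - 1 = 1.4% | 0.90 × 74/75 = 88.8% | 0.50 × 74/75 = 49.3% |
| 3 | 75/72 - 1 = 4.2% | 0.90 × 72/75 = 86.4% | 0.50 × 72/75 = 48.0% |
| 5 | 75/70 - 1 = 7.1% | 0.90 × 70/75 = 84.0% | 0.50 × 70/75 = 46.7% |

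The last column shows the effect on the median: the SAP would report a time at which somewhat fewer than half of all treated subjects are still controlled.

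**Naive-only curve, which the SAP does not plan (N = 26, the ceiling)**
- k = 1: 26/25 - 1 = 4%
- k = 3: 26/23 - 1 = 13%
- k = 5: 26/21 - 1 = 24%

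**Who can be dropped.** Previously treated subjects must not have progressed on siltuximab (Protocol 4.2, criterion 4), so most would already count as controlled, through parent-study response or at extension screening. The exposed group is the naive subjects, for whom SAP 5.2.2.1 looks for control during the extension. Early progression among them is plausible: under the Attachment 2 guide, worsening in any single measure counts as progression.

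**The case against.** Several points on the other side have force.

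- **Screening may qualify subjects.** Investigator assessment is also collected at screening, and the SAP does not exclude it. If stability there counts, few or none are dropped. This stands as a limit on size; the SAP's silence still needs resolving.
- **Early progression does not always mean exclusion.** Protocol 9.3.1 requires discontinuation only after progression at two consecutive assessments. A subject worse at Cycle 4 and stable later would enter. Only never-controlled subjects are lost.
- **It can be read as a deliberate conditional summary.** Its wording is openly conditional, and naive subjects without control remain visible in the proportion under SAP 5.2.2. That helps the reader, but a duration conditional on control should not be timed from before control was documented, and the SAP does not acknowledge a departure from the protocol.
- **The protocol's duration sentence names no population.** True of that sentence alone, but Protocol 11.1 supplies the population for all analyses.

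A reader might infer that the curve is overstated by 13% or 24%, taking 26 as the number of naive subjects. The documents do not support this. The figure is a ceiling inferred from the parent-study allocation, crossover subjects who received siltuximab are no longer naive, and the planned curve is pooled.

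A reader might also fault the SAP for censoring deaths without recorded progression. The protocol's definition is likewise progression only, so this is not an SAP departure.

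**Conclusion.** The point holds as a modest upward bias in a descriptive secondary estimate, and as an inconsistency with Protocol 11.1 and 11.4.1, SAP 2.7 and SAP Section 5. The direction is firm for times after the dropped progressions. The size is not fixed by the documents: 1.4% to 7.1% relative overstatement of the pooled curve if 1 to 5 of 75 subjects are dropped, and close to zero if screening stability qualifies subjects. These figures assume that the dropped subjects progress at their first on-treatment assessment, ahead of other events and censoring.

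It would be tempting to say that early failures in general are lost or that the efficacy result is invalid. Neither follows: previous responders who progress at Cycle 4 can stay in as events, no hypothesis is tested, and the primary objective is safety. The wording should be corrected before the final analysis, but no main conclusion of the study depends on it.

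The parent-study start date for previously treated subjects is a separate matter. They enter only if progression-free, yet time runs from before entry, which also lifts the curve.

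**What to change.** In SAP 5.2.3.1, delete the opening condition that limits the endpoint to subjects with disease control. State that duration of disease control is analysed in all treated subjects, with progression at any extension assessment after first dose, including the first, counted as an event on that date.

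If a controlled-only summary is kept, label it conditional, say whether the screening assessment can establish control, and for naive subjects start the clock at first documented control. For previously treated subjects such a start would be arbitrary, because control was recorded only in the extension.

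Counting death without recorded progression as an event should be offered only as a sensitivity analysis, since making it primary would depart from the protocol definition.

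The cost is SAP wording and minor programming, with no new data. The downside is that reported durations become slightly less favourable. The change does not cure the parent-study time origin, which needs its own decision.
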